### 10.2.3 Rationale for Patient Populations

#### 10.2.3.1 Monotherapy

This is a Phase 1 study evaluating the safety and tolerability of INCB001158 in cancer patients. Since it unknown whether INCB001158 is efficacious, only patients with metastatic disease or advanced disease that is not amenable to local therapy will be enrolled. Further, only patients for whom there are no available therapies that have been shown to provide clinical benefit (e.g., overall survival benefit) will be enrolled. In order to maximize the potential for identifying clinical benefit, the expansion cohorts will enroll tumor types that have been previously shown to have significant infiltration with MDSCs and/or Arg1+ cells. Two monotherapy expansion cohorts identify specific patient populations, NSCLC ([Part 2a](#)) and CRC ([Part 2b](#)), both of which have high infiltration with Arg1+ cells (see Section [10.1.2](#)) and have a large unmet need. An additional expansion cohort ([Part 2c](#)) allows a broader group of patient to be enrolled consisting of tumor types that also have high infiltration of Arg1+ granulocytic MDSCs and PMNs (by

internal data or published accounts), in order to identify a preliminary signal of activity that can be subsequently followed up with a dedicated expansion cohort (or a separate clinical study).

### 10.2.3.2 Combination with Anti-PD-1 (Pembrolizumab)

As of the date when this amendment was authored, the anti-PD-1 agent pembrolizumab has been approved for the treatment of metastatic melanoma, NSCLC, SCCHN, urothelial carcinoma, and solid tumors that are microsatellite instability-high (MSI-H) or mismatch repair deficient (dMMR). Despite the impressive activity observed for this and other anti-PD-1/PD-L1 agents, a majority of patients with these diseases do not achieve an objective response to these agents and there is a recognized need for combination agents to either expand the population that benefits or amplifies the activity that they provide (Melero 2015).

Eight patient populations are eligible to enroll into expansion cohorts, including advanced/metastatic NSCLC (Part 3a), advanced/metastatic melanoma (Part 3b), advanced/metastatic UCC (Part 3c), advanced/metastatic MSI-H CRC (Part 3d), advanced/metastatic MSS CRC (Part 3e), advanced/metastatic gastric /GEJ (Part 3f), advanced/metastatic SCCHN (Part 3g), and advanced/metastatic malignant pleural mesothelioma (Part 3h). Since a primary objective of the expansion cohorts is to identify a signal of clinical activity of INCB001158 in combination with pembrolizumab, some of these cohorts will enroll patients that are unlikely to respond to monotherapy pembrolizumab because they either 1) had disease progression (even after an objective response) in the immediate prior line of therapy, OR 2) had prolonged stable disease ( $\geq 24$  weeks) in the immediate prior line of therapy. The attribution of evidence of clinical activity (e.g., objective responses) to INCB001158 in this population can be made more confidently given the low likelihood of a response to monotherapy anti-PD-1 therapy. In addition to these “add-on” cohorts, other cohorts will enroll patients that have never received prior checkpoint inhibitor therapy. There are generally two reasons to include these cohorts: 1) to identify activity in patient populations that are known to be unresponsive to PD-1 therapy (e.g., MSS CRC) and 2) to identify activity of the INCB001158/pembrolizumab combination that could be missed in pembrolizumab-refractory patients.

All expansion cohorts target tumor types that have a significant proportion of patients with Arg+ infiltrating cells within tumor samples (as presented in Section 10.1) and/or elevated plasma arginase (along with depleted plasma arginine) which may contribute to immune suppression.

## **11.0 PROCEDURES**

All patients must sign an IRB/IEC-approved informed consent prior to starting any protocol-specific procedures, including screening procedures. During the consent process, the person obtaining consent must inform the patient of all elements of informed consent. Patients must also meet the inclusion and exclusion criteria to be enrolled in the study.

### **11.1 Screening Period**

#### **11.1.1 Prior Treatment**

Reasonable efforts will be made during the screening period to determine all prior therapeutic treatments received by the patient. All previous cancer treatments, including systemic therapies, radiation, and/or surgical procedures, should be recorded on the patients' electronic case report forms (eCRFs).

For some patients progressing on pembrolizumab in Parts 3a, 3b, 3c, and 3d, computerized tomography (CT) or magnetic resonance imaging (MRI) scans and/ or radiology reports may be requested for tumor evaluations during the course of prior pembrolizumab or other anti-PD-1 therapy in order to document the status of stable disease and/or progressive disease.

#### **11.1.2 Concomitant Treatment**

Medications or vaccinations specifically prohibited in the exclusion criteria are not allowed during the ongoing trial. If there is a clinical indication for any medication or vaccination specifically prohibited during the trial, discontinuation from trial therapy or vaccination may be required. The investigator should discuss any questions regarding this with the Sponsor Clinical Director. The final decision on any supportive therapy or vaccination rests with the investigator and/or the patient's primary physician. However, the decision to continue the patient on trial therapy or vaccination schedule requires the mutual agreement of the investigator, the Sponsor, and the patient.

### 11.1.2.1 Acceptable Concomitant Medications

Concomitant treatment with other therapies is permitted if the medication is not expected to interfere with the evaluation of safety or efficacy of the study treatments. During the study, if the use of any concomitant treatment becomes necessary (e.g., for treatment of an adverse event), the treatment must be recorded on the appropriate eCRF, including the reason for treatment, name of the drug, dosage, route, and start and stop dates of administration.

*For patients receiving INCB001158 in combination with pembrolizumab (Parts 1b and 3):* In patients that are currently receiving pembrolizumab (Parts 3a, 3b, 3c, and 3d) as part of their prior line of therapy, pembrolizumab should be administered continuously, if possible (i.e., there is no need to discontinue or pause pembrolizumab dosing).

### 11.1.2.2 Prohibited Concomitant Medications

Patients are prohibited from receiving the following therapies during the Screening and Treatment Phase (including retreatment for post-complete response relapse) of this trial:

- Antineoplastic systemic chemotherapy or biological therapy
- Immunotherapy not specified in this protocol
- Chemotherapy not specified in this protocol
- Investigational therapeutic agents other than the study treatments, INCB001158 and pembrolizumab
- Radiation therapy
  - Note: Radiation therapy to a symptomatic solitary lesion or to the brain may be considered on an exceptional case by case basis after consultation with Sponsor. The patient must have clear measurable disease outside the radiated field.
- Live vaccines within 30 days prior to the first dose of trial treatment and while participating in the trial. Examples of live vaccines include, but are not limited to, the following: measles, mumps, rubella, chicken pox, yellow fever, rabies, BCG, and typhoid (oral) vaccine. Seasonal influenza vaccines for injection are generally killed virus vaccines and are allowed. However, intranasal influenza vaccines (e.g. FluMist®) are live attenuated vaccines, and are not allowed.

- Systemic glucocorticoids for any purpose other than to modulate symptoms from an event of clinical interest of suspected immunologic etiology. The use of physiologic doses of corticosteroids may be approved after consultation with the Sponsor.
  - Note: Inhaled steroids are allowed for management of asthma.
- Except for erythropoietin or darbepoetin alpha (Aranesp®), use of growth factors (i.e., G-CSF, GM-CSF, etc.) is not permitted in the first treatment cycle unless the patient experiences a hematologic DLT.
- Concomitant treatment with valproic acid/valproate-containing therapies is not permitted as hyperammonemia is a well-described toxicity of valproic acid, particularly at high exposures, potentially through inhibition of the urea cycle (Verrotti 2002; Wadzinski 2007).
- Concomitant treatment with allopurinol or other xanthine oxidase inhibitors is not allowed during the monotherapy dose escalation of INCB001158 (Part 1a). Xanthine oxidase inhibitors cause an accumulation of OA in the urine, which would confound the assessment of safety in these patients.

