### 5.1.2 Dose-Limiting Toxicity

During dose escalation, patients must receive at least 75% of the planned INCB001158 administrations (Parts 1a and 1b) and two doses of pembrolizumab (Part 1b only) in the DLT evaluation window to be considered evaluable for DLT, unless the patient has a DLT or has the study treatment held for an adverse event (AE) that may herald a DLT. The DLT evaluation window will be the first 28 days (Part 1a) or the first 42 days (Part 1b) on study, starting from Cycle 1 Day 1 (C1D1). Patients who discontinue the study during the DLT evaluation window prior to receiving the requisite study treatment administrations for reasons that include, but are not limited to, clinical/radiographic progression, voluntary withdrawal, or complications that the

Principal Investigator considers secondary to the patient's malignancy will not be considered evaluable for DLT and will be replaced. In addition to DLTs, a pharmacokinetic threshold of 100  $\mu\text{g}\cdot\text{hr}/\text{mL}$  is included as a dose-limiting event. This is an exposure that was well tolerated in preclinical species and exceeds the expected efficacious exposure by 14-fold.

During Part 1b, it is likely that Grade 3 AEs associated with pembrolizumab administration will occur and, given the small sample size of cohorts, this could occur by chance in 2 of 6 patients, the usual threshold for unacceptable toxicity. It will be important to differentiate between immune-related adverse events (irAEs) expected from pembrolizumab toxicity as opposed to an increase in frequency or a worsening of severity of irAEs as an indicator of unacceptable toxicity related to the combination. Dose escalation cohorts can be expanded up to 12 patients if DLTs occur that are expected pembrolizumab-related irAEs per the pembrolizumab product label.

The Common Terminology Criteria for Adverse Events (CTCAE v4.03) will be used to identify and classify toxicities arising during the study. The occurrence of any of the following toxicities during Cycle 1 will be considered a DLT, if judged by the Investigator to be related (possibly or probably) to administration of either or both study treatment(s):

Non- Hematologic DLTs:

- Any  $\geq$  Grade 4 non-hematological toxicity
- Grade 3 non-hematologic toxicity lasting  $> 3$  days despite optimal supportive care with the exception of:
  - Grade 3 fatigue lasting  $\leq 7$  days
  - Grade 3 rash that resolves to  $\leq$  Grade 1 within 3 weeks

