  - Grade 3 tumor flare (defined as local pain, irritation or rash localized at sites of known or suspected tumor)
  - Grade 3 irAE that resolves to Grade 1 with corticosteroid therapy in  $\leq 3$  weeks (Part 1b ONLY)
  - A transient (resolves within 6 hr of onset) Grade 3 infusion-related AE (Part 1b ONLY)
- Any clinically meaningful Grade 3 non-hematologic laboratory value if:
  - Medical intervention (other than electrolyte repletion) is required to treat the patient, OR
  - The abnormality leads to hospitalization, OR
  - The abnormality persists for  $> 1$  week.

Hematologic DLTs:

- Grade  $\geq 3$  febrile neutropenia (ANC  $< 1.0 \times 10^9/L$  with either a single temperature  $\geq 38.3^\circ C$  or a sustained temperature of  $\geq 38^\circ C$  for more than 1 hr)
- Grade 4 neutropenia lasting  $> 7$  days
- Grade 4 anemia
- Grade 4 thrombocytopenia ( $< 25.0 \times 10^9/L$ )
- Grade 3 thrombocytopenia resulting in clinically significant bleeding or requiring platelet transfusion
- Any other  $\geq$  Grade 3 hematologic toxicity

In addition to the DLTs defined above, clear evidence of urea cycle inhibition (e.g., an increase in fasting urinary orotic acid (OA) to  $\geq 10X$  the ULN, any OA value of  $> 40X$  ULN (fasting or non-fasting) or symptomatic hyperammonemia) would also be considered a dose-limiting event and will be monitored closely (see below for urinary OA rationale). Finally, achieving a maximum exposure threshold of an  $AUC_{0-12hr}$  that exceeds  $100 \mu g \cdot hr/mL$  in one patient will limit dose escalation. This exposure is approaching the top of the exposures that were well tolerated in preclinical GLP toxicology studies. Exposure in excess of this threshold will be treated the same as a DLT with regard to the dose escalation rules and definition of the MTD described in Section 5.1.1.

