## 7.2 Exclusion Criteria

1. Any other current or previous malignancy within the past three years except a) adequately treated basal cell or squamous cell skin cancer, b) carcinoma *in situ* of the cervix, c) prostate cancer with stable prostate specific antigen (PSA) levels for 3 years, d) or other neoplasm that, in the opinion of the Principal Investigator and with the agreement of the Medical Monitor, will not interfere with study-specific endpoints.
2. Cytotoxic chemotherapy, tyrosine kinase inhibitor (or other targeted anti-cancer agent), radiation therapy, or hormonal therapy within 14 days or 5 half-lives, whichever is longer, prior to Cycle 1 Day 1 (42 days for nitrosoureas or mitomycin C).

3. Immunotherapy or biological therapy (e.g., monoclonal antibodies) within 21 days prior to Cycle 1 Day 1
  - EXCEPTION: Washout of anti-PD-1 therapy is NOT required in Part 1b Dose Escalation or the Part 3 Expansion Cohorts.
4. Treatment with an unapproved investigational therapeutic agent within 21 days (or 5 half-lives for small molecule agents) prior to Cycle 1 Day 1
  - EXCEPTION: Washout of anti-PD-1 therapy is NOT required in Part 1b Dose Escalation or the Part 3 Expansion Cohorts.
5. Has a diagnosis of immunodeficiency or any condition requiring systemic treatment with either corticosteroids ( $> 10$  mg daily prednisone equivalent) or other systemic immunosuppressive medications within 14 days prior to the first dose of study treatment. Inhaled steroids and adrenal replacement steroid doses  $\leq 10$  mg daily prednisone equivalent are permitted in the absence of active autoimmune disease.
6. Concomitant therapy with valproic acid/valproate-containing therapies.
7. Concomitant therapy with allopurinol and other xanthine oxidase inhibitors
8. Exclusion criterion deleted in Protocol Amendment 2-EU.
9. Patients with symptomatic ascites or pleural effusion requiring intermittent paracentesis or thoracentesis. A patient who is clinically stable following treatment for these conditions (including therapeutic thoraco- or para-centesis) is eligible.
10. Unable to receive medications *per os* (PO)
11. Unstable/inadequate cardiac function:
  - Myocardial infarction or symptomatic ischemia within the last 6 months
  - Uncontrolled or clinically significant conduction abnormalities (e.g., ventricular tachycardia on antiarrhythmics are excluded; 1st degree AV block or asymptomatic LAFB/RBBB are eligible)

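### The xanthine oxidase inhibitor ban covers Part 1a only in Protocol 11.1.2.2 but every part under exclusion criterion 7 and 11.1.2, and the reason given for it applies in every part

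*Protocol*

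**What the plan says.** Three current provisions of the protocol bear on allopurinol and related drugs.

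- **Section 7.2, exclusion criterion 7** (repeated in the Synopsis): "Concomitant therapy with allopurinol and other xanthine oxidase inhibitors". It stands in the general list, not in the separate disease-specific list for Parts 1b and 3, so it applies to every part.
- **Section 11.1.2**: "Medications or vaccinations specifically prohibited in the exclusion criteria are not allowed during the ongoing trial". This carries the criterion past entry and has no part limit.
- **Section 11.1.2.2**, the on-study prohibited list: "Concomitant treatment with allopurinol or other xanthine oxidase inhibitors is not allowed during the monotherapy dose escalation of INCB001158 (Part 1a". The reason follows at once: "Xanthine oxidase inhibitors cause an accumulation of OA in the urine, which would confound the assessment of safety in these patients".

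The bullet directly above the last one bars valproate with no part limit: "Concomitant treatment with valproic acid/valproate-containing therapies is not permitted as hyperammonemia is a well-described toxicity of valproic acid". Section 11.1.2.1 gives the general test for other drugs: "Concomitant treatment with other therapies is permitted if the medication is not expected to interfere with the evaluation of safety or efficacy".

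**The concern.** The prohibited list is where a site will look when a patient needs allopurinol during treatment. A bullet that names Part 1a, directly below one that names no part, reads as a deliberate limit. A site working from that list would conclude that these drugs may be used in Parts 1b, 1c, 2 and 3. A site working from Sections 7.2 and 11.1.2 would conclude that they may not.

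What is at stake is attribution. If a patient outside Part 1a starts a xanthine oxidase inhibitor on study, a rise in urinary orotic acid may come from that drug and not from INCB001158. The protocol uses this marker to interrupt INCB001158 and to consider restarting it at a lower dose.

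**Working it through.** There is no design figure to reproduce. The check has two steps: compare the scope of the three provisions, then ask whether the stated reason is specific to Part 1a.

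**Step 1: scope**

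| Provision | Parts in which the drugs are barred |
|---|---|
| Section 7.2, criterion 7 | All |
| Section 11.1.2, carrying criterion 7 on study | All |
| Section 11.1.2.2 | 1a |

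Valproate (criterion 6) and xanthine oxidase inhibitors (criterion 7) are handled alike in Section 7.2, but differently in adjacent bullets of Section 11.1.2.2. The amendment summaries in Attachments 8 to 12 record no decision to relax the ban outside Part 1a.

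**Step 2: where urinary orotic acid is used for safety**

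*Sampling.* Attachments 1A (Parts 1a and 2) and 1B (Parts 1b, 1c and 3) call for a fasting urine sample on Day 1 of every cycle. Scheduled samples per patient through Cycle 4 Day 1, counted from Attachments 2A to 2C:

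- Part 1a: C1D1 and C1D15, predose and 6 hr (4), plus C1D2, C1D8, C1D22, C2D1, C2D8 predose, C2D8 6 hr, C3D1 and C4D1 (8): 4 + 8 = 12.
- Parts 2a to 2c: C1D1 and C1D15, predose and postdose (4), plus C1D8, C1D22, C2D1, C3D1 and C4D1 (5): 4 + 5 = 9.
- Parts 1b and 3: C1D1 and C1D15, predose and postdose (4), plus C1D8, C2D1, C3D1 and C4D1 (4): 4 + 4 = 8.
- Part 1c: C1D1 predose and 6 hr (2), C1D15 predose and postdose (2), plus C1D8, C2D1, C3D1 and C4D1 (4): 2 + 2 + 4 = 8.

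The Part 2d sampling schedule is redacted and not counted.

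*Dose modification.* Table 12.1-1 is titled as applying to all parts. It calls for interruption when fasting orotic acid exceeds 10 times the ULN, or any value exceeds 40 times the ULN. Restart at a lower dose is then considered with the Medical Monitor.

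*Dose-limiting events.* Section 5.1.2 counts as dose-limiting "clear evidence of urea cycle inhibition (e.g., an increase in fasting urinary orotic acid (OA) to" at least 10 times the ULN, or any value above 40 times the ULN. That section governs Part 1b as well: "The DLT evaluation window will be the first 28 days (Part 1a) or the first 42 days (Part 1b) on study".

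**Result.** Outside Part 1a the marker is measured repeatedly and acted on, so the confounding that justifies the ban can arise in every part. By the test in Section 11.1.2.1, a drug that the protocol itself says confounds the safety assessment would not be acceptable in any part.

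**The case against.** Section 11.1.2.2 never says that these drugs are permitted outside Part 1a. A site that never gives them complies with every provision. The list is also not exhaustive: hormonal therapy (criterion 2) and non-steroid immunosuppressants (criterion 5) are excluded but not named there, so sites must consult Section 11.1.2 in any case. On this view the fault is loose scope wording. The Part 1a limit may even be deliberate or a remnant, because Section 12.1.1 describes urea-cycle monitoring as belonging to Part 1a dose escalation.

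The consequence is also softened by several safeguards. Section 10.1.12 treats orotic acid elevation as a biomarker and not a toxicity. Section 5.1.2 recommends re-testing while dosing continues if there is no clinical sign of urea-cycle inhibition. Section 12.1.3.1 describes the dose rules as guidelines and asks for Medical Monitor contact before a modification. Concomitant drugs are recorded. Section 10.2.2.1 describes dose escalation as complete, with the RP2D declared at 100 mg BID, so the Part 1b dose-limiting rule matters little now.

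The safeguards are real and keep the point minor, although re-testing while the inhibitor continues need not remove the confounding. They do not reconcile the text. An explicit part limit is more than an omission from a list. The Section 12.1.1 wording does not fit the current schedules or Table 12.1-1. If the limit were intended, criterion 7 and Section 11.1.2 would be wrong instead, and the text would still need to change.

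**Conclusion.** The contradiction stands. Section 11.1.2.2 conflicts with Sections 7.2 and 11.1.2 for Parts 1b, 1c, 2 and 3, and with the reason given in the bullet itself. Severity is minor.

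The sample counts show how often the marker is read outside Part 1a. They do not measure harm. The number of patients who start one of these drugs on study is not given, so no affected headcount is stated. No effect on the declared RP2D is claimed. The conclusion assumes that a reader takes the explicit Part 1a limit as the scope of the ban, which is the ordinary reading beside the unlimited valproate bullet.

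**What to change.** In Section 11.1.2.2, delete the words that tie the ban to monotherapy dose escalation in Part 1a, so that the sentence ends at *not allowed*. This matches Sections 7.2 and 11.1.2 and the stated reason. The cost is one deleted phrase, and because entry on these drugs is already barred in all parts, eligibility does not change.

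The alternative is to confine criterion 7 to Part 1a. That would also require a change to Section 11.1.2 and a rule for reading orotic acid in patients taking these drugs. It is more work and goes against the protocol's own reasoning.

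Optionally, in the SAP Appendix A listing of orotic acid, BUN/urea and ammonia, mark values taken during recorded xanthine oxidase inhibitor use. Listing 2.4.7 (prior and concomitant medication) already holds the data needed.

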### 11.1.3 Screening Evaluation

The following screening assessments must be performed **within 21 days** before study treatment administration on C1D1 according to the [Attachment 1](#) [with the exception of imaging (CT/MRI); scans performed within 28 days of study treatment administration on C1D1 are acceptable]. Procedures listed below that are performed as part of the normal standard of care and within 21 days prior to C1D1 may be used for screening purposes:

- Sign and date an IRB/IEC-approved Informed Consent Form (ICF) before any study-specific (i.e., non-standard of care) screening procedures are performed
- Demographic information including date of birth, sex, and ethnic origin
- Medical history including review of prior cancer treatments
- Review of concomitant medications
- ECOG performance evaluation
- Complete physical examination including weight (kg) and height (cm)
- Vital signs and weight

- Standard duplicate 12-lead ECG with corrected QT interval by Fridericia's Formula (QTcF)
- Clinical laboratory evaluation (hematology, coagulation, serum chemistry, and urinalysis); see [Attachment 3](#).
- Serum or urine pregnancy test. This is only required for females of child-bearing potential and must be negative within 3 days prior to C1D1.
- Radiographic evaluation of tumor burden (e.g., diagnostic CT or MRI). Scans performed within 28 days prior to C1D1 will be accepted and do not need to be repeated. See [Attachment 1](#) and [Attachment 2](#). Note: For this study, evaluation of tumor burden must be based on a diagnostic CT or MRI. 1-3 scans prior to the start of study and redacted scan reports will also be collected and sent to a central reader for exploratory evaluation.
- Fresh tumor biopsies: Predose tumor biopsies are required for some patients enrolled in this study. If fresh biopsies are not available at predose, archival tumor tissues, if available, collected within 3 months prior to screening are required. See [Table 11.8-1](#) for additional details. Coagulation tests must be performed and evaluated within 24 hr prior to all biopsy procedures.

A patient who meets all of the inclusion criteria will enter the study. Screen failures will be marked in the electronic data capture (EDC) system.

